5.5.3. Sensitivity Analysis

Time to Clinical Improvement

The following sensitivity analyses will be conducted:

- 1) The primary analysis will be repeated for the PP analysis set.

Change from baseline to Day 10 or hospital discharge if sooner, in the ratio of hemoglobin oxygen saturation to inspired oxygen fraction (SpO₂/FiO₂)

The following sensitivity analyses will be conducted:

- 1) The primary analysis will be repeated for the MITT analysis set.
- 2) The primary analysis will be repeated for the PP analysis set.

Depending on the amount of missing data, additional sensitivity analyses may be needed. If these are needed, they will be documented in the CSR.

5.5.4. Supplementary Analyses

None.

5.6. Secondary Endpoint(s) Analysis

5.6.1. Key/Confirmatory Secondary Endpoint(s)

Change from baseline in serum calprotectin

Both the observed value and the change from baseline value will be summarized. Participants who are discharged prior to day 10, will have their end of treatment assessment, mapped to day 10.

To compare the change from baseline over time a MMRM model will be used. Missing data will be assumed to be missing at random and maintained as missing. The Kenward-Roger method will be used to calculate the denominator degrees of freedom for the test of fixed effects and adjusted standard errors. The model will include baseline value as a covariate, treatment, visit and visit-by-treatment interaction terms as categorical fixed effects, and participant as a random effect. An unstructured covariance matrix will be assumed to model the within-participant errors. This variance-covariance matrix will be estimated across treatment groups. However, if there is a convergence problem with the unstructured covariance matrix, then alternative covariance structures will be examined (heterogeneous Toeplitz structure, Compound Symmetry) and the one with the best fit as determined by the Akaike information criteria (AIC) (i.e., smallest AIC value) will be used. The least squares means (LS-means) for each treatment, LS-means treatment difference and corresponding confidence interval (CI) for the LS-means difference and p-value for the treatment difference, will be reported at each visit. For each parameter, a plot of the LS-means (and 95% CI), over time and by treatment group, will be produced.

5.6.1.1. Sensitivity Analysis

None

5.6.1.2. Supplementary Analyses

None

5.6.2. Supportive Secondary Endpoint(s)

Time to hospital discharge readiness

Time to hospital discharge readiness will be derived as the date of discharge readiness minus the date of randomization. Participants who die/withdraw from the study, prior to discharge, will be censored at day 28. Participants still not ready for hospital discharge at day 28 will be censored at day 28. This endpoint will be analyzed using the same approach as the primary endpoint of time to clinical improvement.

Proportion of participants reporting each 6-point ordinal scale of the clinical status outcome assessment at Days 10/EOT, 14, 21 and 28

The frequency and proportion of participants reporting each score will be reported by treatment group. Participants who are discharged prior to day 10, will have their end of treatment assessment, mapped to day 10. The difference in distributions will be compared between treatment groups using a Cochran-Mantel-Haenszel (CMH) test with Modified ridit scores and stratified by Country (USA, Brazil), age (≤ 65 vs > 65), corticosteroid use (yes vs no) and remdesivir use (yes vs no).

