1.2. Schedule of Activities (SoA)

Table 2: Schedule of Activities

General Notes:

- In case of natural disasters or pandemics, some visits/study procedures can be done via virtual visits (e.g., telemedicine or telephone) or at home visits after hospital discharge. Refer to study reference manual for more details.
- Assessments completed as part of standard of care within the protocol defined windows, will not need to be repeated specifically for the protocol.

Procedure	Screening	Treatment Period			Follow-up			Post-study visit	Notes
		BL	Daily visits [‡]	EOT/ET*			EOS		
Study Day	-3 to -1	1	2-9	10	14	21	28	+60 days from EOS	Baseline (BL); End of Treatment (EOT), Early termination (ET); End of study (EOS) [‡] If a subject is discharged prior to Day 10, they will complete Day 5 and Day 10 visits assessments * This visit will be conducted at hospital discharge, if subject is discharged prior to Day 10
Visit window (days)				±1	±2	±2	±2	±10	
Informed consent	X								
Inclusion and exclusion criteria	X	X							
Demography	X								
Medical history	X								
Current medical conditions	X	X							Including time from onset of symptoms (fever, cough, etc.) to study entry, COVID-19 severity for each subject
Comprehensive physical exam	X			X					
Height and weight	X			X*					*Weight only

Procedure	Screening	Treatment Period			Follow-up			Post-study visit	Notes
		BL	Daily visits [‡]	EOT/ET*			EOS		
Study Day	-3 to -1	1	2-9	10	14	21	28	+60 days from EOS	Baseline (BL); End of Treatment (EOT), Early termination (ET); End of study (EOS) ‡ If a subject is discharged prior to Day 10, they will complete Day 5 and Day 10 visits assessments * This visit will be conducted at hospital discharge, if subject is discharged prior to Day 10
Visit window (days)				±1	±2	±2	±2	±10	
Limited physical exam		X	Day 5		X	X	X		Physical exam will be symptom-directed exam
Hematology	X	X	Day 5	X	X	X	X		Refer to Section 10.2
Clinical chemistries	X	X	Day 5	X	X	X	X		Refer to Section 10.2
INR	X						X		International normal ratio (INR)
Urinalysis	X						X		Refer to Section 10.2
Sputum samples and nasopharyngeal swab for SARS-CoV-2 PCR		X	Day 5	X	X	X	X		Samples to be frozen as specified in the laboratory manual for viral quantification.
Serum hsCRP and ferritin		X	Day 5	X	X	X	X		High sensitivity c-reactive protein (CRP)
Reserve blood sample for biomarker analyses		X	Day 5	X	X	X	X		Date and times to be recorded when samples were collected.
IL-6		X	X	X	X	X	X		Interleukin 6 (IL-6)

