8.1.3. Clinical Status Ordinal Score

Clinical status will be assessed using the 6-point ordinal score (Table 5). The ordinal scale is an assessment of the clinical status at the first assessment of a given study day. Each day, the worse score for the previous day will be recorded. i.e. on day 3, day 2 score is obtained and recorded as day 2. This scale has been used successfully as an endpoint for evaluation of treatments for severe influenza requiring hospitalization (Peterson, 2017).

Table 5: A 6-Point Ordinal Score for Assessing Clinical Status

Score	Description
1	Not hospitalized
2	Hospitalized, not requiring supplemental oxygen
3	Hospitalized, requiring supplemental oxygen
4	Hospitalized, on non-invasive ventilation or high flow oxygen devices
5	Hospitalized, on invasive mechanical ventilation or ECMO
6	Death

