5.1. General Considerations

The following is a list of general reporting conventions:

- Percentages will be based on the number of participants in the analysis set unless otherwise indicated.
- Categorical variables will be summarized using counts (n) and percentages (%) and will be presented in the form of n (%).
- Percentages will be reported to 1 decimal place.
- Continuous data will be summarized using the mean, standard deviation (SD), median, minimum, 25th and 75th percentiles, maximum, and number of participants with data.
- Means and medians will be reported at 1 more significant digit than the precision of the data. Standard deviations and confidence intervals will be reported at 2 more significant digits than the precision of the data. Quartiles, minima and maxima will be reported to the same level of precision as the original observations.
- The median will be reported as the average of the 2 middle numbers if the dataset contains even numbers.
- No preliminary rounding should be performed; rounding should only occur after analysis. To round, consider digit to right of last significant digit: if < 5 , then round down; if ≥ 5 , then round up.
- All p-values will be 1-sided and reported to 3 decimal places (e.g., 0.XXX). Values < 0.001 will be reported as < 0.001 .

If departures from these general conventions are present in the specific evaluations sections of this SAP, then those conventions will take precedence over these general conventions.

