5.2. Visit Windows

The following table outlines the analysis visits that data will be mapped to for analysis of efficacy, safety and pharmacodynamics data collected during the study. If after mapping, multiple data points share the same analysis visit, the data point closest to the expected study visit will be used. If there is a tie, the earlier of the visits will be used.

Study Visit	Analysis Visit	Analysis Window
Screening	Screening	0
Baseline	Baseline	0
Days 1 – 9	Days 1 – 9	0

Day 10	Day 10	± 1 day
Day 14	Day 14	± 2 day
Day 21	Day 21	± 3 day
Day 28/EOS	Day 28	± 3 day
Post Study Visit	Day 88	± 10 day

If Baseline is missing then screening data should be mapped to baseline for analysis purposes.

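### SAP 5.6.2 maps the discharge assessment to Day 10 on the 6-point scale, so participants already at home are tabulated as hospitalized

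*SAP*

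**What the plan says.** SAP 5.6.2 reports the share of participants in each category of the 6-point scale at Day 10/EOT, 14, 21 and 28. It compares arms with a stratified CMH test on modified ridit scores. For Day 10 it adds: "Participants who are discharged prior to day 10, will have their end of treatment assessment, mapped to day 10".

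Protocol 1.2 (Schedule of Activities) says of the EOT/ET visit: "This visit will be conducted at hospital discharge, if subject is discharged prior to Day 10". A second footnote to the same table says: "If a subject is discharged prior to Day 10, they will complete Day 5 and Day 10 visits assessments". It does not say whether those assessments are done on Days 5 and 10 or brought forward to discharge.

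Protocol 8.1.3 describes the scoring in two ways: "The ordinal scale is an assessment of the clinical status at the first assessment of a given study day", and "Each day, the worse score for the previous day will be recorded". Score 1 means out of hospital, score 2 is "Hospitalized, not requiring supplemental oxygen", score 3 is in hospital on supplemental oxygen, and score 6 is death.

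SAP 5.2 has a general rule for duplicate records: "If after mapping, multiple data points share the same analysis visit, the data point closest to the expected study visit will be used".

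**The concern.** The best category on this scale is being out of hospital. A score taken at the discharge visit cannot reach it, because the participant is still an inpatient when scored. Carrying that score to Day 10 places people who are at home in an in-hospital category. Two further consequences follow.

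- A participant sent home on oxygen (3) ranks below one still in hospital on room air (2).
- Someone who leaves on Day 6 and is readmitted or dies on Day 8 keeps the favourable discharge score at Day 10.

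The endpoint is the set of category proportions, so the Day 10 table is wrong whatever the test shows. If the drug mainly shortens hospital stay, the comparison at that visit can lose much of the signal.

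**Working it through.** **1. What score the mapping yields**

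- SAP 5.6.2: the Day 10 value of an early-discharged participant is the EOT assessment.
- Protocol 1.2: that assessment is made at discharge.
- Protocol 8.1.3, first rule (first assessment of the day): the participant is still in hospital, so the score is at least 2.
- Protocol 8.1.3, second rule (worst score of the day): part of the day was in hospital, so the score is again at least 2.
- Protocol 8.1.5 records whether the participant left with oxygen. One who did scores 3.
- No sentence in the SAP resets the score to 1 for those at home, or to 6 for those who died after discharge.

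**2. How many could be affected**

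The plan gives no figure for this scale, so I borrow the design assumptions for time to clinical improvement (SAP 3): placebo median 12–15 days, time halved on active, 2:1 allocation, two-sided 5%. They reproduce. With θ = ln 0.5, d = (1.96 + 0.842)² / [(1/3)(2/3)(0.693)²] ≈ 73.5, or 74 events against 75 stated, and 75 events give 80.8% power.

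With exponential times, the share improved before Day 10 is 1 − 2^(−9/median):

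- Placebo, median 12: 1 − 2^(−0.75) = 41%. Median 15: 1 − 2^(−0.6) = 34%.
- Active, median 6: 1 − 2^(−1.5) = 65%. Median 7.5: 1 − 2^(−1.2) = 56%.

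These are upper bounds for the share re-scored, because improvement also counts coming off oxygen while still in hospital.

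**3. What it does to the test**

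The documents give no ordinal distribution and no home-oxygen rate, so the following are assumptions. Percentages run over scores 1 to 6, with 80 active and 40 placebo, an unstratified rank test and one-sided 2.5%. Mapping moves every score 1 to 2, or 80% of them to 2 and 20% to 3.

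| | Placebo | Active | Power, true status | Mapped, all on room air | Mapped, 20% on oxygen |
|---|---|---|---|---|---|
| A | 37/10/33/8/6/6 | 60/8/20/5/4/3 | 66% | 59% | 42% |
| B | 37/20/25/8/5/5 | 57/8/20/6/5/4 | 34% | 12% | 6% |
| C | 37/5/38/8/6/6 | 58/10/19/6/4/3 | 66% | 73% | 59% |

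Repeat runs move these by about one percentage point.

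The direction can be read from the distributions. If all leave on room air, mapping merges scores 1 and 2, so the discharge gap vanishes and the off-oxygen gap (scores 1 + 2) remains.

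- A: discharge gap 60 − 37 = 23 points; off-oxygen gap 68 − 47 = 21.
- B: discharge gap 57 − 37 = 20 points; off-oxygen gap 65 − 57 = 8. Most of the signal goes.
- C: discharge gap 58 − 37 = 21 points; off-oxygen gap 68 − 42 = 26. Merging helps slightly.

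Two further sets of simulations (4,000 trials each) give the extremes. If 70% are off oxygen in both arms and 60% vs 35% are discharged, so that the benefit is on discharge alone, power falls from about 40% to 3% or less. If the benefit is on oxygen need and all leave on room air, power is 57–70% on true status and 62–72% mapped, so nothing is lost.

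**The case against.** The strongest reply is that the plan may already pick up a true Day 10 record. The second schedule footnote has early-discharged participants complete Day 10 assessments. SAP 5.2 operates after mapping and keeps the record nearest the planned visit, so a real Day 10 record would displace the mapped one. This stands as a possibility. It is not settled, because the other footnote moves the visit to discharge and SAP 5.6.2 states its mapping without exception. Two programmers could produce different Day 10 tables.

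A reader might try to close that gap with SAP 5.1, where section-specific departures are handled by the words "then those conventions will take precedence over these general conventions", and infer that the EOT mapping must override SAP 5.2. The documents do not support this. The sentence concerns the 5.1 list (percentages, rounding, decimals, p-values), and the visit-window rule is in a separate section.

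A second reply is that the SAP heads this timepoint Day 10/EOT, so the mapping is deliberate. That shows intent, but a scale whose best category is being out of hospital is not informative when read at the moment of leaving it.

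Third, the consequence is limited. One visit of one supportive secondary endpoint is affected, earlier discharge enters the primary time-to-recovery endpoint, and time to discharge readiness is analysed separately. This stands in full.

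**Conclusion.** The point holds for the 6-point scale at Day 10. As written, the mapping tabulates early-discharged participants as hospitalized and drops death or readmission between discharge and Day 10. On the design medians, at most 34–41% of placebo and 56–65% of active participants are re-scored. This assumes exponential times and that every improvement is a discharge. Whether it happens in practice depends on which of two unreconciled rules is programmed.

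A reader might infer that the mapping always biases the comparison towards no effect. It does not: assumed distributions give 66% vs 42–59% and 34% vs 6–12%, but also 66% vs 73%. A benefit on oxygen need still shows as 2 against 3 or higher. The supportable statement is that a discharge benefit at Day 10 can be hidden. The power figures are illustrations, and their test omits the four stratification factors in SAP 5.6.2.

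A reader might also extend the criticism to IL-6, D-dimer, calprotectin and viral load, which use the same mapping. That is not supported. The SAP labels those timepoints 10/EOT, and dosing stops at discharge, so an end-of-treatment sample is a coherent choice. Days 14, 21 and 28 are not mapped. The correction should be made, but it does not touch the primary analyses.

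**What to change.** In SAP 5.6.2, for the 6-point scale only, replace the mapping with status on Study Day 10:

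- 1 if alive and out of hospital
- the observed score if readmitted
- 6 if dead

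State that this overrides the EOT mapping for this scale, and how it relates to the closest-record rule in SAP 5.2. Leave the mapping for SpO2/FiO2, which is defined as Day 10 or discharge, and for the 10/EOT biomarker and viral-load timepoints.

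The cost is a few sentences and a short derivation, to be settled before database lock. Discharge and readmission dates (protocol 8.1.5) and deaths (protocol 8.3.6) are already collected. The one gap is a participant readmitted by Day 10 with no score recorded that day. The dates show hospitalization but not the level of support, so the SAP should say how that case is scored.

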Hospital discharge readiness assessment		X	X	X	X	X	X		Refer to Section 8.1.5
Clinical status 6-point ordinal scale	X	X	X	X	X	X	X		Refer to Section 8.1.2
State of consciousness	X	X	X	X	X	X	X		Level of consciousness: alert (A), arousable only to voice (V), or pain (P) and unresponsive (U)

Procedure	Screening	Treatment Period			Follow-up			Post-study visit	Notes
		BL	Daily visits [‡]	EOT/ET*			EOS		
Study Day	-3 to -1	1	2-9	10	14	21	28	+60 days from EOS	Baseline (BL); End of Treatment (EOT), Early termination (ET); End of study (EOS) [‡] If a subject is discharged prior to Day 10, they will complete Day 5 and Day 10 visits assessments * This visit will be conducted at hospital discharge, if subject is discharged prior to Day 10
Visit window (days)				±1	±2	±2	±2	±10	
Randomization		X							
Study drug administration		X	X	X					Treatment to be administered during hospitalization only
Study drug accountability			X	X					
AE and SAE review		X	X	X	X	X	X		Adverse event (AEs), Serious AE (SAEs)
Prior and concomitant medication	X	X	X	X	X	X	X		
Survival status					X	X	X	X	

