
 Additional efficacy outcomes 	
 Mortality rate during the 28-day study period following enrollment Time to hospital discharge readiness Proportion of subjects ready to be discharged from the hospital during the 28-day study period following enrollment Proportion of subjects with resolution of fever below entry criteria for 24 hours (as defined in Section 5.1.1) by Day 10 in subjects with fever at baseline Time to resolution of fever below entry criteria for 24 hours (as defined in Section 5.1.1) in subjects with fever at baseline Duration (in days) of remdesivir use in subjects starting remdesivir within 24 hours of first dose of BLD-2660 Change from baseline to Days 10, 14, 21 and 28 in clinical status outcome using a 6-point ordinal scale (Section 8.1.3) Proportion of subjects reporting each 6-point ordinal scale of the clinical status outcome assessment Change from baseline to Days 5, 10, 14, 21 and 28 in NEWS score Change from baseline to Days 10, 14, 21 and 28 in IL-6 and D-dimer
Exploratory	

 Other efficacy outcomes 	
 Proportion of subjects who require mechanical ventilation after study entry Number of ventilator-free days to Day 21 Proportion of subjects with ICU transfer and/or ventilator dependence during the 28-day study period following enrollment

Objectives	Endpoints
	
 • The time to a NEWS of ≤ 2 and maintained for 24 hours • Change in NEWS from baseline to Days 3, 5, 8, 10, 14, 21 and 28 in NEWS

 • To evaluate antiviral activity of BLD-2660 in the same population 	
 • Proportion of subjects who are SARS--CoV-2 virus free by Day 10/EOT or hospital discharge, whichever is sooner • Time to eradication of SARS-CoV-2 • Change from baseline in SARS-CoV-2 viral load at Days 5, 10, 14, and 28

 • Other safety outcomes 	
 • Clinically relevant changes from baseline in electrocardiogram (ECG), and clinical laboratory values at each post baseline timepoint • Proportion of subjects with clinically significant drug-related troponin elevations that have repeat elevation upon confirmatory testing as adjudicated by the DMC while continuing on study drug during the 10-day treatment period

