5. STUDY POPULATION

5.1. Eligibility Criteria

5.1.1. Inclusion Criteria

To be eligible for participation in this study, subjects must meet all the following:

Age

1. At least 18 years of age at the time of signing the ICF.

Type of Subject and Disease Characteristics

2. Hospitalized for COVID-19.
3. Diagnosed with COVID-19 as defined by having at least 2 of the following signs or symptoms within the past 2 days:
 - a. Fever defined as a body temperature of ≥ 38.0 °C oral, or ≥ 38.3 °C rectal, ≥ 37.7 °C forehead or ≥ 38.7 °C aural (axillary temperatures are not allowable);
 - b. Cough;
 - c. Fatigue;
 - d. Shortness of breath.
4. Radiographic evidence (chest x-ray or CT scan) of one the following:
 - a. Ground-glass opacities, or
 - b. Local or bilateral patchy infiltrates, or
 - c. Interstitial pulmonary infiltrates.
5. Oxygen requirements:
 - a. $SpO_2 \leq 94\%$ on ambient airOR
 - b. Requires supplemental oxygen administration by nasal cannula, simple face mask, or other similar oxygen delivery device.

Sex

6. Male and/or female subjects.

Contraception use by men or women should be consistent with local regulations regarding the methods of contraception for those participating in clinical studies.

7. All subjects (male or female) who are of childbearing potential must agree to use highly effective contraception during the study. Female subjects and male partners of female subjects must continue to use highly effective contraception for 30 days after the last dose of study drug. Female subjects should not donate oocytes during this time. Male subjects and female partners of male subjects must continue to use highly effective contraception for 90 days. Male subjects must agree not to donate sperm during this time.

Note: Abstinence is acceptable if this is the usual lifestyle and preferred contraception for the subject.

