Change from baseline in SARS-CoV-2 viral load at Day 10/EOT (or hospital discharge, whichever is sooner and end of study (Day 28) will be analyzed using an MMRM model.

The proportion of patients reporting each of the categories using the 6-point ordinal scale will be compared between treatment groups using the CMH test.

The change from baseline in the NEWS score will be summarized at each time point. A comparison between treatment groups will be made using an MMRM model.

The following secondary endpoints: number of O_2 supplementation free days, change from baseline in clinical status using 6-point ordinal scale (Table 5), and improvement (i.e., change) from baseline as measured by the ratio of hemoglobin oxygen saturation to inspired oxygen fraction ($\text{SpO}_2/\text{FiO}_2$) using the 4-point ordinal scale (Table 4) will be summarized using descriptive statistics and comparisons between treatment groups made using appropriate statistical methods.

The mean SpO_2 for subjects not requiring oxygen supplementation at Days 5, 10, 21 and 28 will be summarized using descriptive statistics.

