5.8.3. Safety Labs.....	22
5.8.4. Vital Sigs.....	22
5.8.5. 12-Lead ECG	23
5.8.6. Physical Exam.....	23
5.9. Other Analyses.....	23
5.9.1. Pharmacokinetic Analyses	23
5.9.2. Pharmacodynamic Analyses	23
5.9.3. Subgroup Analyses	24
5.9.4. Demographics and Baseline Characteristics	24
5.9.5. Medical History	24

CONFIDENTIAL

Statistical Analysis Plan [Version 3.0]

5.9.6.	Concomitant Medications	25
5.9.7.	Compliance	25
5.10.	Interim Analyses	25
6.	References.....	29

CONFIDENTIAL

Statistical Analysis Plan [Version 3.0]

Version History

This Statistical Analysis Plan (SAP) for study B-2660-204 is based on the protocol version 3.0 amendment 2.0, dated May 8th, 2020.

SAP Version	Approval Date	Change	Rationale
1.0	30 August 2020	Not Applicable	Original version
2.0	08 October 2020	Subjects who die or withdraw prior to observing clinical improvement should be censored at Day 28 instead of date of death or withdrawal	Implemented change at the request of FDA. FDA reviewed version 1.0 and provided comments on 22 September, 2020
		All modeling was clarified to indicate that all covariates would be entered into the model at the beginning and the stepwise selection procedure would be used to assess inclusion of these covariates.	
		For all models, corticosteroid use (yes vs no) was added as a potential covariate to include in the stepwise model selection process.	
		In the analysis of the exploratory endpoint of proportion of subjects who are SARS-CoV-2 virus free at Day 10/EOT or hospital discharge, whichever is sooner, subjects who die/withdraw from the study prior to Day 10/discharge will be classified as a non-responder instead of using their last known value.	

CONFIDENTIAL

Statistical Analysis Plan [Version 3.0]

		
For Poisson Regression models, if overdispersion exists, a negative binomial model will be used and a model where the option to adjust the standard errors using the scale parameter will not be run.
	
		
Removed a number of secondary and exploratory efficacy analyses
	
Based on the DSMB recommendation to not expand the study, a number of efficacy analyses were removed to preserve capital

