3.0	22 October 2020	
Added additional details on how to derive FiO2 values based on oxygen flow rates.
 
Changed IL-6 sub-group analysis from > ULN to > median,
	
eCRFs collected flow rate or FiO2. Additional details on how to derive FiO2 were needed for programming.
 
IL-6 values do not have normal ranges

1. Introduction

This Statistical Analysis Plan (SAP) contains a more technical and detailed elaboration of the principal features of the analysis described in the protocol and includes detailed procedures for executing the statistical analysis. This SAP should be used in conjunction with the protocol. If there are any discrepancies between the protocol and SAP, this SAP will prevail. Any deviations from this SAP that are implemented in the final analysis will be documented with sound clinical and statistical rationale in the Clinical Study Report (CSR). In the event of any changes to the primary endpoints or analyses, these changes will be documented through a protocol amendment, consistent with ICH E9.

A separate document contains the table, figure and listing specifications and any example programming codes.

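### No retained analysis of the 6-point clinical status endpoint uses the baseline 6-point score, so a valid test carries avoidable noise and chance baseline imbalance

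*SAP*

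**What the plan says.** - **Planned test.** SAP 5.6.2 reports the distribution over the six categories at Days 10/EOT, 14, 21 and 28. It compares arms with a CMH test on modified ridit scores, "stratified by Country (USA, Brazil), age (≤ 65 vs > 65), corticosteroid use (yes vs no) and remdesivir use (yes vs no". That is four binary factors, or 16 cells. The section names no sensitivity or supplementary analysis of this endpoint.
- **Collection.** The Schedule of Activities (Protocol 1.2) has a row for "Clinical status 6-point ordinal scale" marked at Screening, at baseline on Day 1 and at each later visit to Day 28.
- **What the protocol had.** Protocol 3 listed a change from baseline "in clinical status outcome using a 6-point ordinal scale (Section 8.1.3", and Protocol 9.4.2 planned to summarize and compare "change from baseline in clinical status using 6-point ordinal scale (Table 5". For the category proportions, Protocol 9.4.2 says only that they "will be compared between treatment groups using the CMH test" and names no baseline score.
- **What the SAP kept.** SAP 1.1 lists only the proportions in each category. The version history records: "Removed a number of secondary and exploratory efficacy analyses". The Introduction adds: "If there are any discrepancies between the protocol and SAP, this SAP will prevail".
- **Other outcomes.** The SAP models for SpO2/FiO2, viral load, calprotectin, IL-6 and D-dimer all include the baseline value.

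**The concern.** Participants need not enter at the same level. Protocol 5.1.1 criterion 5 admits people on ambient air with SpO2 of 94% or below (score 2), and anyone who "Requires supplemental oxygen administration by nasal cannula, simple face mask, or other similar oxygen delivery device" (score 3). High-flow oxygen is not named, but neither the phrase about similar devices nor the exclusions (FiO2 of 0.75 or more; required or expected mechanical ventilation) clearly rules it out, so score 4 is possible.

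Under the planned test, a participant at score 2 on Day 10 counts the same whether entry was at 2 or at 4. Randomization is stratified by remdesivir only, so nothing in the design balances oxygen status between 80 and 40 people. What is at stake is precision, and how far one realized imbalance could colour the result. This is the retained secondary efficacy endpoint in which death is an outcome level.

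**Working it through.** **1. The plan's own figures.** Neither document gives power for the 6-point endpoint. The sample size comes from the co-primary endpoints. For SpO2/FiO2 (SAP 3: difference 25, SD 40, 80 vs 40, two-sided 5%):

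Φ(25 / [40·√(1/80 + 1/40)] − 1.96) = Φ(3.23 − 1.96) = 89.8%, against the stated 90% or so.

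The 80:40 split is taken as given below.

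**2. Chance imbalance.** If a share p enters at score 4 (assumed), the arm difference in that share has SD √[p(1−p)(1/80 + 1/40)].

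| p | SD (points) | 95% range (points) |
|---|---|---|
| 0.10 | 5.8 | ±11.4 |
| 0.25 | 8.4 | ±16.4 |
| 0.40 | 9.5 | ±18.6 |

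**3. Gain from baseline, latent-normal simulation.** Assumptions, none from the documents: entry scores 2/3/4 at 15/65/20%, a latent treatment shift of 0.55 SD, and correlation ρ between baseline and outcome. 4,000 trials per setting, randomized 2:1 within remdesivir stratum, modified-ridit CMH, one-sided 2.5%.

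| ρ | Remdesivir only | Remdesivir × baseline | Gain (points) |
|---|---|---|---|
| 0.3 | 68.3% | 69.6% | 1.3 |
| 0.5 | 69.6% | 75.3% | 5.7 |
| 0.7 | 69.5% | 82.0% | 12.5 |

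Null rejection at ρ = 0.5 was 2.6% without and 2.0% with baseline. Allowing for variation between simulations of this kind, the gain is about 0–1, 5–6 and 12–14 points.

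**4. Comparison with the SAP's actual strata.** A second simulation generated outcomes from a proportional-odds model. Assumptions: entry scores at 15/60/25%; Day 10 scores 1–6 at 50/12/18/8/7/5% at reference covariate values; treatment odds ratio 3.5; remdesivir without effect. 2,000 trials per row; entries are power in %.

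| Baseline log-odds per point | SAP 16 cells | 16 cells × baseline (48) | Remdesivir only | Remdesivir × baseline |
|---|---|---|---|---|
| 0 | 82.2 | 71.1 | 87.4 | 86.2 |
| 0.7 | 80.6 | 70.7 | 86.2 | 86.2 |
| 1.2 | 76.6 | 71.0 | 81.3 | 85.6 |
| 1.8 | 70.2 | 70.7 | 76.2 | 84.1 |
| 2.5 | 54.0 | 65.8 | 60.6 | 81.1 |

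- *Effect of baseline* (last column minus the one before): −1.2, 0.0, +4.3, +7.9, +20.5 points.
- *Effect of fewer strata* (remdesivir only minus 16 cells): +5.2, +5.6, +4.7, +6.0, +6.6 points, with no baseline information used.
- *Baseline as a fifth factor* (48 minus 16 cells): −11.1, −9.9, −5.6, +0.5, +11.8 points. About 32 of 120 participants fall in cells containing one arm only, against about 8 with 16 cells.
- *Type I error* (nominal 2.5%): 1.7–2.8% for 16 cells, 2.0–3.2% for remdesivir only, 2.2–3.2% for remdesivir × baseline. Monte Carlo SE is √(0.025 × 0.975/2000) = 0.35 points.
- *Proportional-odds model* with all four SAP factors, without versus with baseline: 86% vs 84% at 0.7, 79% vs 90% at 1.2, 77% vs 87% at 1.8 (122–136 trials each, error 3–4 points).

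**5. The SAP's test under the step 3 assumptions**, with no prognostic effect given to the other factors. The 16-cell test had 60%, 59% and 60% power at ρ = 0.3, 0.5 and 0.7. Remdesivir × baseline had 68%, 71% and 81%. A rank regression keeping every SAP factor plus baseline gave similar figures to the latter.

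**The case against.** **The test is valid.** Treatment is randomized, and the error rate already covers chance imbalance. A reader might infer that the omission biases the comparison; the documents do not support that, and the null simulations contradict it. What remains is conditional. In null simulations under similar assumptions, about 7% of trials had a mean baseline favouring active by more than 1.5 SD. In those trials the unadjusted test rejected 7.5%, 11.3% and 15.6% of the time at ρ = 0.3, 0.5 and 0.7. With baseline score in the strata, rejection was 3.1%, 2.4% and 3.2%.

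**Baseline does not fit into the planned strata.** This stands. As a fifth factor it costs power unless it is very strongly prognostic. Any fix that replaces the strata also drops country, age and corticosteroid use, and corticosteroid use was deliberately added to the models in SAP version 2.0. That choice has to be stated.

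**The size is assumed.** This stands too. The entry mix and ρ appear nowhere in the documents, and score 4 at entry is an inference. A reader might apply the continuous-outcome formula, Φ((1.96 + 0.84)/√(1 − 0.5²) − 1.96) = 89.9%, and claim a rise from 80% to 90% at ρ = 0.5. The ordinal simulation at the same ρ gives only about 6 points.

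**A pre-dose Day 1 score is not assured.** Protocol 8.1.3 refers both to the first assessment of the day and to recording the previous day's worst score, so the Day 1 value may include time after dosing. The fix must allow for this.

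**Consistency and weight.** The outcomes that adjust for baseline are analysed with MMRM. The SAP's other CMH endpoint (mechanical ventilation) and its Cox endpoints carry no baseline severity term, so consistency alone is a weak argument. The endpoint is supportive, has no power claim and bears on no success criterion.

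**Conclusion.** The omission is real: the baseline score is scheduled, the protocol's change-from-baseline endpoint on this scale is not in the SAP, and no retained analysis of the scale uses baseline. The cost is efficiency and exposure to chance imbalance, not validity. Against a remdesivir-only CMH test, the gain from baseline itself is about 0–1 power points at ρ = 0.3, 5–6 at 0.5 and 12–14 at 0.7, given the assumed entry mix. It approaches zero if nearly everyone enters at score 3.

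A reader might attribute the whole gap between the SAP's 16-cell test and the remdesivir × baseline test (8, 12 and 21 points in step 5) to the missing baseline score. That would be wrong, because anything beyond the gain just stated comes from having fewer strata. The change is worth making because the score is already collected and the cost is low. The primary conclusions do not depend on it.

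**What to change.** In SAP 5.6.2, at each day, do one of the following:

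1. Fit a proportional-odds model with treatment, baseline 6-point score and the randomized remdesivir stratum. Keep age, country and corticosteroid use as covariates if the sponsor wants them. Report the common odds ratio with its 95% CI.
2. Use the modified-ridit CMH test stratified by baseline score (2, 3, 4) × remdesivir stratum only, six cells at most, and state that the other three factors are dropped.

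Do not add baseline score to the existing four factors.

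Define baseline as the last assessment before the first dose, and use the Screening score if the Day 1 value is not clearly pre-dose. SAP 5.2 already maps Screening to baseline when baseline is missing, so this extends an existing rule.

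Cost: a short change to the analysis paragraph and the baseline definition, with no new data. A sparse baseline level may need pooling with its neighbour. If baseline proves uninformative, the loss in the simulation was about one point (87.4% vs 86.2%).
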